2.2. Scientific Rationale

The test product formulation is based on the most promising clinical research on natural ingredients to safely impact the immune system and reduce duration of the common cold. While the evidence to support the use of these individual active ingredients is growing, well-designed human clinical trials showing benefit are necessary to demonstrate efficacy of the test product's unique formulation.

The present study will include at least 200 adult participants in the general population who are seeking herbal remedies to reduce the duration of their common cold symptoms.

2.2.1.Potential Risk

Minimal risk is foreseen for participants through their participation in the study. All the ingredients composing the test product are Generally Recognized as Safe (GRAS) by the FDA for daily consumption at their present concentrations.

The ingredients in the test product have shown to have some theoretical drug interactions which have been listed in the appendix.

Potential side-effects have been observed in high doses which are significantly greater than the dose of the capsule as recommended in the instruction for use:

- · epigastric pain
- nausea
- vomiting
- loss of appetite
- abdominal cramps
- diarrhea
- headaches

This study is determined by Sponsor and Principal Investigator to be a Minimal Risk Study.

Minimal risk is defined by 45 U.S. Code of Federal Regulations (CFR) 46.102 (i) as follows:

"Minimal risk means that the probability and magnitude of harm or discomfort anticipated in the research are not greater in and of themselves than those ordinarily encountered in daily life or during the performance of routine physical or psychological examinations or tests."

Refer to: http://www.hhs.gov/ohrp/humansubjects/guidance/45cfr46.htm#46.102

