Participants will be recruited via digital advertisements. Ads will target those who are prone to getting the common cold; travelers, healthcare providers, teachers, daycare workers, etc.

After clicking on an advertisement, potential participants will then be directed to a website where they will complete a screening questionnaire (See Appendix). The screening questionnaire will

automatically qualify or disqualify them for study participation. If the participant qualifies, she will be provided an informed consent. Upon completion of the informed consent they will be deemed enrolled in the study.

5.2.Inclusion/Exclusion Criteria

Prior to being enrolled, participants will fill out a screening questionnaire. The screening questionnaire will automatically qualify or disqualify them for study participation. The full screening questionnaire can be found in the Appendix.

Inclusion Criteria:

Adult candidates in the general population who are in good health and are seeking herbal remedies to reduce the duration of their common cold symptoms when they should arise. Participants will be deemed to be in good health if they do not report any of the medical conditions asked about in the screening questionnaire.

Exclusion Criteria:

- Age < 18 years old
- Unwilling to try the test product during their first cold experience in the trial
- Has any of the following medical conditions:
 - Allergy to any of the following ingredients: Echinacea, Ivy Extract, Camu Camu, Vitamin C, Ginger, Turmeric, Zinc or a known allergy to Guar Gum, Monk Fruit, Citric Acid, Natural Flavors.
 - Alcohol consumption more than 10 drinks per week
 - Chronic renal disease
 - Chronic liver disease
 - Known autoimmune or immunodeficiency disorders
 - Pregnant or breastfeeding

6.Study Evaluation

6.1.Study Procedures

- Candidates will review information about the study and complete a screening form.
- During the screening process, the participant will be asked questions regarding their symptoms and medical history to ensure that they meet the requirements to participate in this study. The potential participant will also be asked questions to ensure that they do not meet any of the exclusion criteria and meet all of the inclusion criteria.
- After successful screening (participant does not meet any exclusion criteria), participants will
 review and sign study informed consent.
- Upon verification of signed informed consent, participant will be enrolled into the study.

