Echinacea appears to inhibit intestinal cytochrome P450 3A4 (CYP3A4), leading to an increase in oral midazolam availability. Echinacea also appears to induce hepatic CYP3A4, increasing hepatic clearance of midazolam by 34%. Overall, plasma levels of midazolam after oral administration do not seem to be affected by echinacea. However, theoretically, echinacea might decrease the effectiveness of intravenous midazolam by inducing hepatic CYP3A4 and lowering plasma levels by about 20% (12155).

WARFARIN (Coumadin)

Interaction Rating = **Minor** Be watchful with this combination.

Severity = Insignificant • Occurrence = Possible • Level of Evidence = **B**

Preliminary clinical research in healthy male volunteers suggests that taking echinacea increases the clearance of the active S-isomer of warfarin after a single dose of warfarin, but there was not

a clinically significant effect on the international normalized ratio (INR) (20083). Patients taking warfarin should be advised to use echinacea cautiously.

Interactions with Herbs & Supplements

None known.

IVY EXTRACT

There are no Serious Drug Interactions known for Ivy Extract.

None known.

Interactions with Herbs & Supplements

None known

ACEROLA, VITAMIN C

There are no Serious Drug Interactions known for Acerola. There are a couple theoretical Moderate Interactions having to do with its Vitamin C content, however.

ESTROGENS

Interaction Rating = **Minor** Be watchful with this combination.

Severity = Mild • Occurrence = Possible • Level of Evidence = **D**

Concomitant use of estrogens with acerola might increase absorption and therapeutic effects due to vitamin C content $(\underline{129,130})$.

FLUPHENAZINE (Prolixin)

Interaction Rating = **Moderate** Be cautious with this combination.

Severity = Moderate • Occurrence = Possible • Level of Evidence = **D**

Concomitant use with acerola decreases blood levels due to vitamin C content (15).

WARFARIN (Coumadin)

Interaction Rating = **Moderate** Be cautious with this combination.

Severity = High • Occurrence = Possible • Level of Evidence = **D**

Concomitant use with acerola can reduce anticoagulant activity of warfarin due to its vitamin C content (506).

Interactions with Herbs & Supplements

VITAMIN C: Due to vitamin C content in acerola, concomitant use of acerola with vitamin C supplements might increase the risk of adverse effects associated with vitamin C.

GINGER

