There are no Serious Drug Interactions known for Ginger. There are some theoretical Moderate Interactions having to do with the potential of ginger in decreasing platelet aggregation. See Below for List.

ANTICOAGULANT/ANTIPLATELET DRUGS

Interaction Rating = **Moderate** Be cautious with this combination. Severity = High • Occurrence = Possible • Level of Evidence = **B**

Based on laboratory research, ginger is thought to inhibit thromboxane synthetase and decrease platelet aggregation (7622,12634,20321,20322,20323,96257). However, this has not been demonstrated unequivocally in humans, with mixed results from clinical trials (96257). Theoretically, excessive amounts of ginger might increase the risk of bleeding when used with anticoagulant/antiplatelet drugs. Some anticoagulant or antiplatelet drugs include aspirin, clopidogrel (Plavix), dalteparin (Fragmin), enoxaparin (Lovenox), heparin, ticlopidine (Ticlid), warfarin (Coumadin), and others.

ANTIDIABETES DRUGS

Interaction Rating = **Minor** Be watchful with this combination. Severity = Moderate • Occurrence = Unlikely • Level of Evidence = **D**

Evidence from animal and human research suggests that ginger might increase insulin levels and/or decrease blood glucose levels (12636,20402,20403,20404,20405,89895,89896). Theoretically, ginger might have an additive effect with antidiabetes drugs and cause hypoglycemia. Some antidiabetes drugs include glimepiride (Amaryl), glyburide (DiaBeta, Glynase PresTab, Micronase), insulin, metformin (Glucophage), pioglitazone (Actos), rosiglitazone (Avandia), and others.

CALCIUM CHANNEL BLOCKERS

Interaction Rating = **Minor** Be watchful with this combination.

Severity = Moderate • Occurrence = Unlikely • Level of Evidence = **D**

Preliminary research suggests ginger might have hypotensive and calcium channel-blocking effects (12633). Theoretically, ginger might have an additive effect with calcium channel blockers. Calcium channel blockers include nifedipine (Adalat, Procardia), verapamil (Calan, Isoptin, Verelan), diltiazem (Cardizem), isradipine (DynaCirc), felodipine (Plendil), amlodipine (Norvasc), and others.

CYCLOSPORINE (Neoral, Sandimmune)

Interaction Rating = Minor Be watchful with this combination.

Severity = Mild • Occurrence = Possible • Level of Evidence = **D**

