In an animal model, ginger juice taken 2 hours prior to cyclosporine administration reduced the maximum concentration and area under the curve of cyclosporine by 51.4% and 40.3%, respectively. This effect was not observed when ginger juice and cyclosporine were administered at the same time (20401).

METRONIDAZOLE (Flagyl)

Interaction Rating = **Minor** Be watchful with this combination.

Severity = Mild • Occurrence = Possible • Level of Evidence = **D**

In an animal model, ginger increased the absorption and plasma half-life of metronidazole. In addition, the elimination rate and clearance of metronidazole was significantly reduced (20350).

NIFEDIPINE

Interaction Rating = **Moderate** Be cautious with this combination.

Severity = Moderate • Occurrence = Possible • Level of Evidence = **B**

Clinical research shows that combined treatment with ginger 1 gram plus nifedipine 10 mg significantly inhibits platelet aggregation compared to nifedipine alone or ginger alone (20324).

PHENPROCOUMON

Interaction Rating = **Moderate** Be cautious with this combination.

Severity = High • Occurrence = Possible • Level of Evidence = **D**

Phenprocoumon, a warfarin-related anticoagulant used in Europe, might increase the international normalized ratio (INR) when taken with ginger. There is one case report of a 76 year old woman with a stable INR on phenprocoumon that increased to greater than 10 when she began consuming dried ginger and ginger tea (12880).

WARFARIN (Coumadin)

Interaction Rating = **Moderate** Be cautious with this combination. Severity = High • Occurrence = Possible • Level of Evidence = **B**

Preliminary evidence suggests that ginger might inhibit thromboxane synthetase and decrease platelet aggregation (7622,12634,20321,20322,20323). In one case report, ginger increased the INR when taken with phenprocoumon, which has similar pharmacological effects as warfarin (12880). In another case report, ginger increased the INR when taken with a combination of warfarin, hydrochlorothiazide, and acetaminophen (20349). A longitudinal analysis suggests that taking ginger increases the risk of bleeding in patients taking warfarin for at least 4 months (20348). However, research in healthy people suggests that ginger has no effect on INR, or the pharmacokinetics or pharmacodynamics of warfarin (12881,15176). Until more is known, monitor INRs closely in patients taking significant amounts of ginger.

Interactions with Herbs & Supplements

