ANTICOAGULANT/ANTIPLATELET HERBS AND SUPPLEMENTS: Based on laboratory research, ginger is thought to inhibit thromboxane synthetase and decrease platelet aggregation (7622,12634,20321,20322,20323). However, this has not been demonstrated unequivocally in humans with mixed results from clinical trials (96257). Concomitant use of ginger with other herbs that might affect platelet aggregation could theoretically increase the risk of bleeding in some people. These herbs include angelica, clove, danshen, garlic, ginkgo, Panax ginseng, red clover, turmeric, and others.

HERBS AND SUPPLEMENTS WITH HYPOGLYCEMIC POTENTIAL: Ginger might increase insulin levels and/or decrease blood glucose levels (12636,20402,20403,20404,20405,89895,89896). Theoretically, ginger might have additive effects with herbs that decrease blood glucose levels. Herbs with hypoglycemic potential include devil's claw, fenugreek, guar gum, Panax ginseng, and Siberian ginseng.

TURMERIC

There are no Serious Drug Interactions known for Turmeric. There are some theoretical Moderate Interactions, however, see below for list.

ANTICOAGULANT/ANTIPLATELET DRUGS

Interaction Rating = **Moderate** Be cautious with this combination. Severity = High • Occurrence = Possible • Level of Evidence = **D**

In vitro, turmeric has been shown to have antiplatelet effects (11143,81204,81271). However, results from human research are inconsistent. Turmeric has reportedly increased in the international normalized ratio (INR) in a patient using the vitamin K antagonist, fluindione (89718). However, use of a whole food supplement containing broccoli powder, turmeric

powder, pomegranate whole fruit powder, and green tea extract for 6 months does not influence INR in men taking warfarin (89730). Also, combining curcumin 500 mg with aspirin 100 mg does not appear to increase antiplatelet effects or bleeding risk (96137). Until more is known, use turmeric cautiously in combination with anticoagulant and antiplatelet drugs. Theoretically, concomitant use might increase the risk of bleeding due to decreased platelet aggregation. Some of these drugs include aspirin, clopidogrel (Plavix), dalteparin (Fragmin), enoxaparin (Lovenox), heparin, ticlopidine (Ticlid), warfarin (Coumadin), and others.

ANTIDIABETES DRUGS

Interaction Rating = **Moderate** Be cautious with this combination. Severity = Moderate • Occurrence = Possible • Level of Evidence = **B**

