13.1.3. Appendix C Screening Form

Screening

- 1. Are you at least 18 years old? (DOB?) (Y/N)
- 2. Have you ever been diagnosed with any chronic liver disease? (Y/N)
- 3. Have you ever been diagnosed with any chronic renal disease? (Y/N)
- 4. Are you pregnant or breastfeeding? (Y/N)
- 5. Do you have any allergies to any of the following? (Y/N)
 - a. Echinacea
 - b. Ivy Extract
 - c. Camu Camu
 - d. Vitamin C
 - e. Ginger
 - f. Turmeric
 - g. Zinc
 - h. Monk fruit
 - i. Guar Gum
 - j. Citric Acid
 - k. Natural Flavoring
- 6. Have you ever been diagnosed with an autoimmune or immunodeficiency disease? (Y/N)
- 7. Do you have more than 10 alcoholic beverages per week? (Y/N)
- 8. Are you willing to try the test product for relief of your symptoms? (Y/N)
- 9. Are you comfortable taking your own temperature with a digital thermometer? (Y/N)

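### Appendix A urges caution with anticoagulant and antiplatelet drugs, but the eligibility screen never asks about current medication and no review of medication answers is stated before product ships

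*Combined protocol and SAP*

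**What the plan says.** Section 2.2.1 says that the ingredients have "some theoretical drug interactions which have been listed in the appendix" and gives no rule for handling them. In Appendix A, three entries bear directly on the product's ginger and turmeric. Each is rated Moderate, with severity High and occurrence Possible:

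- Ginger with anticoagulant or antiplatelet drugs (evidence level B): "Theoretically, excessive amounts of ginger might increase the risk of bleeding when used with anticoagulant/antiplatelet drugs".
- Ginger with warfarin (level B): "Until more is known, monitor INRs closely in patients taking significant amounts of ginger".
- Turmeric with anticoagulant or antiplatelet drugs (level D): "Until more is known, use turmeric cautiously in combination with anticoagulant and antiplatelet drugs".

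A fourth entry is supporting only: "Concomitant use with acerola can reduce anticoagulant activity of warfarin due to its vitamin C content" (same rating, level D). It is written for acerola, which is not an ingredient, although the mechanism it gives is vitamin C content and each packet supplies 500 mg of vitamin C. The echinacea–warfarin entry is rated Minor.

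On eligibility, section 5.2 states: "The screening questionnaire will automatically qualify or disqualify them for study participation". It also defines health by the same form: "Participants will be deemed to be in good health if they do not report any of the medical conditions asked about in the screening questionnaire". Section 4.2 withdraws a participant who is prescribed any medication, from the date of that prescription. Section 6.1 lists medications among the baseline topics and ships product once staff confirm that the baseline assessment is complete. The section 6.2 schedule has a Meds & Supplements row, marked in the column before product receipt.

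**The concern.** The protocol identifies a combination that calls for caution, but shows no step that would find the people to whom the caution applies. Section 2.2.3 opens its account of risk minimisation with careful screening; for this risk, the screening form shown has no content.

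The rules also treat like cases differently. Someone newly prescribed warfarin during the trial is withdrawn under section 4.2, while someone already established on it qualifies. No reason is given for the difference.

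The later safeguards act only after exposure: the daily side-effect question in Appendix E, the bleeding prompts in Appendix G, and the advice in section 6.4 to stop and seek care. At stake is a participant on an anticoagulant or antiplatelet drug who takes two herbs that Appendix A links to platelet effects. Each herb's entry names the other as a possible additive source, and the plan states no point at which the investigator decides whether that is acceptable.

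**Working it through.** The plan gives no figure on this point, so the check is mainly a cross-reading, followed by simple exposure arithmetic.

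1. **Exclusions (5.2).** These cover age under 18, unwillingness to try the product, ingredient allergy, alcohol above 10 drinks a week, chronic renal disease, chronic liver disease, autoimmune or immunodeficiency disorder, and pregnancy or breastfeeding. None concerns medication.

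2. **Screening form (Appendix C).** The nine items cover age, liver, kidney, pregnancy or breastfeeding, allergy, immune disease ("Have you ever been diagnosed with an autoimmune or immunodeficiency disease"), alcohol, willingness, and use of a thermometer. Items on current medication: 0 of 9. No cardiac or clotting condition is asked about either, so the definition of good health does not remove these users indirectly.

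3. **Baseline (6.1 and 6.2 against Appendix D).** The text promises medication capture. On the form shown, item 5 (medication) and item 6 (supplements) are both limited to what is taken during a cold. A person on daily warfarin could truthfully leave it out.

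4. **Shipment (6.1).** The condition is that the assessment is complete. No review of the answers is described, and no answer stops shipment.

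5. **During the trial.** The wording of section 4.2 deals with being prescribed something and does not clearly reach treatment already running at entry. Appendix E item 11 asks about a prescription only after a doctor's visit for the cold symptoms.

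6. **Dose.** From the Supplement Facts panel and the twice-daily schedule in section 4.1:
   - Ginger: 2 × 250 mg = 500 mg a day; 36 packets × 250 mg = 9 g at most.
   - Turmeric powder: 2 × 500 mg = 1,000 mg a day; 36 × 500 mg = 18 g at most.
   - Appendix A does not say what amount of ginger counts as significant or excessive.

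7. **Number exposed.** The documents give no share of users, so p is an assumption. Inputs: 200 enrolled (5.1) and 40% with a cold (7.2). Sent product = 200 × p; expected to dose = 200 × p × 0.40.

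| Assumed p | Sent product | Expected to dose |
|---|---|---|
| 0.5% | 1 | 0.4 |
| 2% | 4 | 1.6 |
| 5% | 10 | 4 |
| 10% | 20 | 8 |

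At the overrun limit in section 5.1, 1.25 × 200 = 250, so p of 2% to 10% gives 5 to 25 people sent product. That limit rises if the target is recomputed. The good-health criterion may push p toward the low end; no upper age limit is stated. These are counts of exposure, not of harm.

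**The case against.** The strongest reply is that the plan does commit to learning about medication before anyone is exposed. Section 6.1 names medications separately from the treatment of previous colds, section 6.2 schedules their capture before receipt, and section 7.3 plans baseline medications as a covariate. A reader might infer from the screening form that product is posted with nobody knowing what the participant takes. The documents do not support that. They show a commitment in the text, a narrower form, and no stated rule for acting on the answers.

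Nor does absence from the appendices prove that no form exists: the cold start form required by sections 4 and 6.1 is not there either. The consent text and the welcome-package sheet are not shown and may carry a warning. A warning would help, but it would be neither a screening item nor a hold on shipment.

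A reader might also infer that the combination is known to be harmful. Appendix A does not say so:

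- It lists no serious interactions for ginger or turmeric, and reserves its instruction not to combine for cephalexin.
- On ginger, it reports no effect on INR or on warfarin kinetics in healthy people, but also case reports of raised INR and a longitudinal signal of more bleeding in warfarin users.
- On turmeric, it reports one raised INR with fluindione, but no influence on INR of a turmeric-containing supplement taken for 6 months by men on warfarin, and no apparent added bleeding risk with curcumin plus aspirin.

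Finally, the lack of clinic visits does not mean that INR goes unchecked, because nothing in the protocol suspends a participant's usual care.

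These points limit the claim. They do not close the gap between the advice in Appendix A and the eligibility rule, which admits established users without asking.

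**Conclusion.** The point holds as a gap in risk minimisation. The stated automatic rule qualifies a person on established warfarin or clopidogrel, the baseline form shown need not reveal the drug, and no one is assigned to act on the answer before product ships. Harm is not shown, and a rating of Moderate with advice to be cautious does not by itself require exclusion.

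The number affected cannot be derived from the documents. The range of 1 to 20 people sent product rests on an assumed share of 0.5% to 10% of 200. The 0.4 to 8 expected to dose also assumes that users catch colds and start the product at the protocol's overall rate of 40%. The conclusion about the rules does not depend on either assumption. It does depend on Appendices C and D being the forms in use, and unseen forms or consent text could narrow the gap. It is worth correcting because the correction is cheap.

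**What to change.** 1. Add to Appendix C: *Do you currently take a blood thinner or antiplatelet drug (e.g. warfarin, clopidogrel, daily aspirin)?* A yes neither qualifies nor disqualifies automatically, and section 5.2 should say so. Product is held until the investigator records a decision to release or exclude; without a recorded decision, nothing ships.
2. Widen Appendix D item 5 to all current medication, so that it matches sections 6.1 and 6.2.
3. At the existing pre-shipment confirmation, have those answers checked against Appendix A, with any listed drug referred to the investigator. This also covers other entries rated severity High, such as immunosuppressants with echinacea.

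The cost is one new question, one reworded item, a short review for those who answer yes or report a listed drug, and the loss of a few candidates. Review of a yes is best done before consent: each participant excluded after enrolment would remove 1 × 0.40 = 0.4 expected treated participants from the desired 80, which the planned sample-size check at 180 enrolled can absorb. A side benefit is usable data for the baseline-medication covariate, which section 7.3 plans only if suitable data exist.
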